# I. Hypotheses and Specific Aims

The central hypothesis is that inhibitory insular TMS can be used to provide a non-invasive intervention to decrease nicotine craving, alter resting state brain connectivity, and reduce craving-associated insular activity in smokers. All experiments will be conducted in treatment-seeking smokers. These experiments are designed to evaluate the efficacy of insular neuromodulation using rTMS. Outcome measures include (1) cigarette craving measures, (2) resting-state fMRI connectivity measures, and (3) tasked-based fMRI insular activity measures. In a double-blinded two-arm (sham rTMS and inhibitory insular rTMS) randomized control trial with 20 smokers assigned to each arm, we will collect craving measurements, resting state fMRI, and task-based fMRI before and after a single session of rTMS treatment to investigate the following aims:

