insula may be more important in "toggling" away from DMN and toward ECN. To date only one paper describes rTMS specifically targeting the insula: a study of seven patients, reporting subjective changes in cold perception and tolerance of the intervention. Dinur Klein et al. applied high-frequency, low-frequency, and sham rTMS to the bilateral DLPFC with some magnetic field spread into the anterior insulae bilaterally. They reported high-frequency bilateral stimulation significantly reduced cigarette consumption and nicotine dependence, with significantly increased levels of abstinence both immediately after the treatment and at 6 months follow-up. No fMRI data were obtained. The major weakness of the Dinur-Klein et al study is that it primarily targeted the DLPFC, with minimal excitatory posterior treatment coverage of the insula. Given the salience toggling hypothesis, to optimally modulate craving therapies one should provide either excitatory stimulation to the DLPFC or inhibitory stimulation of the insula. *While most experts in this field acknowledge the critical role of the insula in nicotine dependence, there has been surprisingly little research exploring neuromodulation of the insula as a potential therapy.* 

This proposal seeks to answer several questions: (1) Can inhibitory TMS be used to reduce cigarette craving in smokers? (2) Can inhibitory insular TMS alter insular connectivity and activity? And, (3) does inhibitory insular TMS alter brain-behavior relationships? The literature implicating the insula in maintenance of craving in smokers suggest rTMS targeting the insula may provide a more robust modulation of nicotine craving.

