Task-based fMRI exams will be preprocessed as above. Data will be modeled in SPM8 using a GLM with customized square waveforms representing the condition (i.e., cigarette versus neutral stimulus) and duration of stimulus convolved with a canonical hemodynamic response function.

Contrast maps of smoking>neutral cues will be analyzed using second-level random-effects to compare these contrasts within and between treatment groups using ANCOVA. Two separate task-based analyses will be performed: (1) insular ROI analyses by extracting insular activity from the fMRI with a 5mm radius sphere centered at the insular TMS target, and (2) whole brain analysis. Both analyses will control for multiple comparisons using cluster-based correction for family-wise error p<0.05. These comparisons will provide results for **Aim #3**.

C.8 Resting state network analysis (secondary): One inherent limitation of the seed-based connectivity approach is that the resultant connectivity maps are highly dependent upon ROI selection. To circumvent the potential interference caused by seed selection, secondary investigation of the functional connectome will be performed using group independent component analysis to make inferences using the GIFT toolbox (http://icatb.sourceforge.net) and using the same method and analysis pipeline as our preliminary data. Resultant resting state network connectivity maps will be compared by group to investigate differences in strength and direction of connectivity between salience, default mode, and executive control networks.

C.9 Brain-behavior relationships (secondary): Secondary analysis of brain-behavior relationships will be conducted using a GLM in SPM8 by regressing insular connectivity and activity (see C.3.6) against craving and dependence measures. This will characterize the relationship between behavior (**Aim #1**) and brain function (insular connectivity [**Aim #2**] and activity [**Aim #3**]).

C.10 Relative concentrations of GABA, glutamate, and glutamine after rTMS (exploratory): Exploratory analysis of the changes in GABA, glutamate, and glutamine concentrations induced by rTMS will be performed using spectroscopic peak detection methods and ANCOVA.

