# E. Potential Scientific Problems:

I have experience conducting both structural and function neuroimaging experiments. Nonetheless, this study has potential pitfalls. One limitation is that insular rTMS may also stimulate the lateral inferior frontal gyrus; by design, any rTMS treatment can also affect structures superficial to the target along the  $\vec{B}$  trajectory. This potential pitfall can be easily addressed by correlating craving measures with (1) exploratory seed-based connectivity and (2) ROI based activity of all structures included in the rTMS field. Such exploration would determine if other structures showed altered connectivity/activity after insular rTMS, as well as determine if brain-behavior relationships in other structures were altered by insular rTMS. Another potential limitation is that the effect of insular rTMS may manifest only as changes in insular connectivity but not insular activity – we address this predicament by investigating both.

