# F. Data Analysis Plan:

# F.1 Aim 1: Determine if insular TMS reduces cigarette craving:

F.1.1 Statistical Design: For a multivariate analysis of covariance model, we will fit a general linear multivariate model, with measures of craving before and after treatment as the outcomes. As predictors, we will fit indicator variables for treatment assignment, and FTND. We will use the Hotelling-Lawley test to assess treatment by time interaction, and the main effects of time and treatment.

F.1.2 Sample Size and Power Analysis: Li et al. conducted an experiment similar to ours, measuring craving responses to DLPFC rTMS (Cohen's d = 3.0) or sham TMS (Cohen's d = 1.9).

Based on these estimates, we will need to recruit 15 subjects to each arm (total n=30) to detect similar differences with 80% power and 0.05 significance level. Our study should achieve similar power, even with up to 25% loss to follow-up in each arm. If our loss-to-follow up is only 10% per arm, we can detect an effect size as small as 0.962 with 80% power and 0.05 significance level. Our sample size is larger or similar to other studies using similar methods.

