# F.2 Aim 2: Determine if insular TMS alters insular connectivity:

F.2.1 Statistical Design: A second-level random effects model will be used to compare insular connectivity by treatment and group using ANCOVA. Age will be controlled for as nuisance variables. A Monte Carlo cluster correction threshold will be applied to correct for multiple comparisons, using a voxel-wise p<0.005 and family-wise p < 0.05.

F.2.2 Sample Size and Power Analysis: Hanlon et al. measured fMRI connectivity changes after rTMS to two separate prefrontal targets, resulting in Cohen's *d* values greater than 1.9. Based on these estimates, our target recruitment goal must be greater than 6 in each arm (total n=12) to detect significant differences with 80% power and 0.05 significance level. Our sample size n=32 (after 10% attrition of fMRI data, 10% attrition of TMS administration) is similar or larger compared to other studies using similar methods. With a sample size of 32, we can detect a correlational effect size as small as 0.30 ( $f^2$ ) with 80% power and 0.05 significance level.

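### The brain-behavior analysis in C.9 does not say how treatment arm or time point enters, so as written it does not answer whether rTMS alters the relationship

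*Combined protocol and SAP*

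**What the plan says.** The closing paragraph of Section II lists three study questions. The third is "does inhibitory insular TMS alter brain-behavior relationships". Section E returns to it for tissue lying over the target: correlating craving with imaging there is meant to "determine if brain-behavior relationships in other structures were altered by insular rTMS".

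The corresponding analysis is C.9 in Section IV, labelled secondary. It is a general linear model in SPM8, carried out "by regressing insular connectivity and activity (see C.3.6) against craving and dependence measures". Its stated purpose is descriptive: "This will characterize the relationship between behavior" and brain function. It does not mention treatment arm, an interaction, separate slopes by arm, or whether pre-treatment, post-treatment or change values are used. No section numbered C.3.6 appears in the document, so the cross-reference does not supply these details. Section F covers Aims 1 to 3 and contains no brain-behavior model.

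On size, the trial plans two arms "with 20 smokers assigned to each arm". For imaging, F.2.2 gives "Our sample size n=32 (after 10% attrition of fMRI data, 10% attrition of TMS administration"), and adds: "With a sample size of 32, we can detect a correlational effect size as small as 0.30" (f²).

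**The concern.** To ask whether treatment alters a relationship is to ask whether the slope of imaging on craving differs between active and sham. A single slope over all subjects averages the two arms. It can be near zero when treatment has reversed the relationship, and clearly non-zero when treatment has changed nothing.

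There is a second, conditional problem. H1 to H3 predict that active rTMS moves both craving and insular imaging. If both variables in the regression are measured after treatment, or as change, and both differ between arms, pooling links them through arm alone. A reader could then take the result as craving tracking insular function from subject to subject when no such tracking exists within either arm.

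At stake is one of the three questions posed in Section II, and the interpretation of a secondary result. The analyses of Aims 1 to 3 are not affected.

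**Working it through.** **Inputs.** N=32 for imaging (F.2.2: 40 × 0.9 × 0.9 = 32.4), taken as 16 per arm; the equal split is an assumption. Two-sided 5% tests (sidedness is not stated). Craving difference 0.962 SD, the minimum detectable effect in F.1.2 ("we can detect an effect size as small as 0.962 with 80% power and 0.05 significance level"), or 3.0 − 1.9 = 1.1 from the per-arm values cited there. Connectivity 1.9, the lower bound cited in F.2.2. Treating 0.962, 1.1 and 1.9 as active-versus-sham differences in this trial is an assumption.

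**The plan's own figure.** For one correlation in 32 subjects, the Fisher z approximation gives a minimum r = tanh[(1.96 + 0.84)/√29] = 0.478, so f² = r²/(1 − r²) = 0.296. The stated 0.30 reproduces. It describes a single pooled correlation, not a difference between two slopes.

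**Check 1: does the pooled slope answer the question?** Normal data were simulated at 16 per arm with no arm difference in means. The pooled correlation test was compared with the craving-by-arm interaction.

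| True r, one arm / other arm | Pooled test significant | Interaction significant |
|---|---|---|
| +0.5 / −0.5 (reversed) | about 7% | about 81-82% |
| 0.5 / 0.5 (unaltered) | about 85% | about 4-5% |
| 0.5 / 0 (abolished) | about 29% | about 28% |

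The first two rows are decisive. The pooled test almost always misses a reversal and usually reports significance when nothing has changed.

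**Check 2: association created by the arm difference.** With zero correlation within each arm, equal arms, and between-arm differences d₁ and d₂ in SD units, the pooled correlation is

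r = (d₁d₂/4) / √[(1 + d₁²/4)(1 + d₂²/4)].

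For d₁=0.962 and d₂=1.9: 0.457 / √(1.231 × 1.9025) = 0.30.

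| d craving / d connectivity | Induced r | Pooled test significant |
|---|---|---|
| 0.3 / 0.3 | 0.02 | about 5% |
| 0.5 / 0.5 | 0.06 | about 6% |
| 0.962 / 0.962 | 0.19 | about 18-19% |
| 0.962 / 1.9 | 0.30 | about 40-41% |
| 1.1 / 1.9 | 0.33 | about 49% |
| 0 / 1.9 | 0 | about 5% |

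With an arm term in the model, the rate was about 5% in every scenario run with it (all rows except 0.3 / 0.3). The last row shows that both variables must differ between arms for the effect to arise.

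**Check 3: what the interaction can detect.** At 16 per arm, 80% power needs a Fisher z difference of (1.96 + 0.84) × √(2/13) = 1.10. That corresponds to r=+0.50 against −0.50, or 0.80 against 0.

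**The case against.** The strongest reply is that C.9 is one sentence about a general linear model, and such a model can hold arm and interaction terms. The other imaging analyses do compare groups (C.6, C.7, C.8, F.2.1, F.3.1), so the authors may intend the same here. This stands in part: C.9 is silent on treatment and does not exclude it. A reader might infer that the plan prescribes a pooled slope; the text does not say so. The defect is lack of specification, and it matters because an analyst who follows C.9 literally fits a model that does not answer the question.

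A reader might also infer that any brain-behavior association from C.9 would be an artefact of the arm difference. The documents do not support that. C.9 names no time point. C.2 makes the QSU-Brief the only survey repeated after treatment, and A.1 asks whether characteristics assessed before treatment go with later connectivity change. Under randomization, baseline predictors do not differ by arm in expectation, so pooling creates no spurious slope for them.

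Nor do the higher percentages describe expected behaviour. The 1.9 comes from a cited study of other stimulation targets, 0.962 is a minimum detectable effect, and 1.1 is a between-arm difference only if the two cited values share a standardizer. Moderate differences give almost no inflation.

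Finally, a pooled association is real covariation in the sample; it misleads only if read as coupling within arms. That is fair, and C.9 does not claim within-arm coupling. But the pooled association still does not answer the question in Section II.

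**Conclusion.** The concern holds as a gap in specification. Sections II and E ask whether treatment alters a relationship, C.9 does not say how treatment or time enters, and nothing in Section F fills the gap. Without arm, the fitted slope does not address the question: about 7% against about 81% for a full reversal, and about 85% pooled significance when nothing is altered. These figures assume 16 per arm and normal data, but no arm difference in means.

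The spurious-association problem is narrower. It applies only where post-treatment or change scores are used on both sides and both differ between arms. Its size runs from about 5-6% at 0.3-0.5 SD to 40-49% if the cited connectivity value and a craving difference of 0.962-1.1 are taken as between-arm effects. It does not apply, in expectation, to dependence and trait scales collected only before treatment.

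Because C.9 is secondary, this is an inexpensive improvement to the plan and no threat to the primary aims.

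**What to change.** In C.9, state that change in insular connectivity (and, separately, activity) is regressed on arm, change in craving, and arm-by-change in craving. Use the interaction to address the third question of Section II, and the arm-adjusted slope as the brain-behavior association. For baseline dependence and trait measures, use arm, the measure, and arm-by-measure. Apply the same form to the overlying structures in Section E, add the model to Section F, and correct the C.3.6 cross-reference.

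The cost is two degrees of freedom and no new data. Adding the interaction corrects the question being tested but does not supply power: at n=32 it has about 28% for r=0.5 against 0. The plan should therefore commit to reporting the slope in each arm and their difference with confidence intervals, labelled exploratory, and a non-significant interaction should not be read as evidence that the relationship is unaltered.

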# D. Description, Risks and Justification of Procedures and Data Collection Tools:

Risks Associated with TMS

- 1. **Headaches (common).** The risk of headaches or scalp discomfort is approximately 10%. This discomfort is self-limited and responds to over the counter analgesics (e.g., ibuprofen, aspirin, or acetaminophen).
- 2. Seizures (rare). When used within parameters set by recent consensus statements, the risk of seizures is less than 1 in 1,000. Seizures reported have been self-limited. The lifetime incidence of seizures in the US population is 10%. Isolated self-limited seizures do not cause brain injury or other adverse effects to the subject, are painless, and do not have known adverse effects on health. There have been no reported cases of status epilepticus (uncontrollable seizure which can be disabling or life-threatening) or epilepsy (recurrent, unprovoked seizures) following TMS. When evaluating subject risk per the standardized COMIRB review procedure for TMS studies, studies with a low (<1%) risk of a single selflimited seizure should not be considered a serious risk to the health of a subject. In addition, according to the COMIRB Guidelines for TMS Protocol Evaluation, studies with stimulation parameters within the Wasserman criteria and low frequency (≤1 Hz) are likely safe without need for IDE or further FDA evaluation. Because this study will use a low frequency single train rTMS (1 Hz) within Wasserman criteria, ensure adequate hearing protection, administer neurological examinations before and after rTMS treatment, and monitor subjects by a medical doctor ([name]) during and for at least 60 minutes after rTMS treatment, we do not feel that an FDA IDE is required. This opinion is consistent with the aforementioned guidelines and COMIRB TMS review guidelines (our decision pathway is highlighted in blue):

[name] will be present throughout the subject's participation and for 60 minutes after the completion of the TMS treatment (during MRI scans). He will monitor for signs of seizure or muscle twitching. [name] is a physician trained in seizure management and will have ready access to life-support equipment (oxygen, suction, blood pressure monitoring, CPR equipment) and antiepileptic drugs.

- 3. **Hearing loss (rare)**. The risk of hearing loss is well below 1 in 10,000 and appears to be completely avoidable with appropriate hearing protection (ear plugs). All subjects are required to wear the standard-of-care hearing protection. Subjects are asked to report to study staff immediately if their hearing protection becomes loose or is otherwise inadequate. In addition, study staff will monitor all subjects to ensure compliance with hearing protection.
- 4. **Movement or heating of metallic objects (rare).** TMS may cause heating or movement of intracranial metal, such as in subjects with implantable electrodes, cerebrospinal fluid shunts, skull plates, or other intracranial metal. These subjects will be excluded.
- 5. **Damage to electronic medical devices (rare).** TMS may interfere with electronic medical devices such as pacemakers, implantable stimulators, or implantable pumps. These subjects will be excluded.
- 6. **Pregnancy (rare).** There is not sufficient data to assess the safety of TMS in pregnancy, although TMS has been performed in limited numbers of pregnant subjects without adverse effects. Pregnant subjects will be excluded.

Risks Associated with MRI

7. **Movement or heating of metallic objects** (rare, serious). The only known hazard associated with exposure to a static high magnetic field is that the magnet exerts a strong force on ferromagnetic objects. For this reason, ferromagnetic objects are excluded from the vicinity of the magnet so that they will not become projectiles. At the Brain Imaging Center, the research MRI for human use has a field strength of 3.0 T. Imaging at these field strengths is not considered a significant risk according to FDA guidelines. The scanning sequences applied are within the FDA guidelines for human MR scanning. In addition, every subject undergoes an extensive safety screening to determine whether

he/she has any implanted materials, objects, device, or dental retainers that may pose a risk. If there is any doubt about the nature of any implanted material, or any other contraindication to MR scanning, the subject will not be scanned.

- 8. Damage to electronic medical devices (rare, serious). See #7.
- 9. **Pregnancy** (rare, serious). Any woman who reports being pregnant or reports that they may be pregnant will be excluded from this study. Any woman of childbearing age who reports that she is not pregnant will undergo a urine pregnancy screen. Those who test positive will be excluded from participating in this study.
- 10. **Claustrophobia** (common). If patients are anxious they can be trained in the mock scanner located adjacent to the MR scanner to mitigate anxiety and help the subject adjust to the scanning environment. Subjects who want to quit immediately or who are otherwise not interested in participating in this study can do so at any time, and this option will be discussed with the subject during informed consent and at regular intervals thereafter.
- 11. **Nausea** (rare). Rarely, subjects may become nauseated as a result of the alternative magnetic fields or acoustic noise. Subjects are able to terminate participation in the study at any time.
- 12. **Irritation from loud sounds** (common). Loud sounds occur during functional MRI scanning. They are unpleasant, but not loud enough to be harmful. All subjects will wear standard-of-care ear protection while undergoing the MRI scans. Subjects are able to terminate participation in the study at any time.

# General Risks Associated with Research Participation

- 13. **Potential risk of loss of confidentiality (rare).** This study includes drug screening, alcohol screening, and pregnancy test assessment. There is the potential that this information may not be kept confidential, such as in theft of study material.
- 14. **Fatigue (common).** Tiredness or boredom may occur during behavioral tasks and the MRI scan. Subjects are able to terminate participation in the study at any time.
- 15. **Frustration (common).** Subjects may become frustrated while performing the craving-cue task in the MRI scanner. Subjects are able to terminate participation in the study at any time.

# E. Potential Scientific Problems:

I have experience conducting both structural and function neuroimaging experiments. Nonetheless, this study has potential pitfalls. One limitation is that insular rTMS may also stimulate the lateral inferior frontal gyrus; by design, any rTMS treatment can also affect structures superficial to the target along the  $\vec{B}$  trajectory. This potential pitfall can be easily addressed by correlating craving measures with (1) exploratory seed-based connectivity and (2) ROI based activity of all structures included in the rTMS field. Such exploration would determine if other structures showed altered connectivity/activity after insular rTMS, as well as determine if brain-behavior relationships in other structures were altered by insular rTMS. Another potential limitation is that the effect of insular rTMS may manifest only as changes in insular connectivity but not insular activity – we address this predicament by investigating both.

